## V. OVERVIEW OF STUDY DESIGN

The proposed comparative effectiveness study is a multicenter, randomized, double-blind clinical trial that will use a 2 x 2 factorial design to assess the effectiveness of IV isotonic sodium bicarbonate compared to IV isotonic saline and NAC compared to placebo for the prevention of serious, adverse, patient-centered outcomes in high-risk patients undergoing coronary or non-coronary angiography. The primary hypotheses to be tested are that isotonic bicarbonate is more effective than saline and that NAC is more effective than placebo for the prevention of serious morbidity and mortality following coronary and non-coronary angiography in high-risk Veterans. Each of these two hypotheses are of equal importance as there is clinical equipoise on both the comparative effectiveness of bicarbonate and saline and the benefit of NAC. Moreover, despite the lack of any data establishing the efficacy of NAC in the absence of concomitant IV fluids, our data indicate that as many as 12% of high-risk Veterans receive this anti-oxidant in lieu of any IV fluids (*vide supra*). We believe that the beneficial effects of these interventions on adverse outcomes will be mediated through a reduction in the development of CIAKI.

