**Model 2**

|         | Bicarbonate | Saline |       |  |
|---------|-------------|--------|-------|--|
| NAC     | 5.59%       | 7.46%  | 6.52% | } Overall event rate
7.6% |
| Placebo | 7.46%       | 9.95%  | 8.70% |  |
|         | 6.52%       | 8.70%  |       |  |

Most trials have reported effect sizes for the outcome of CIAKI rather than for our defined 90 day primary composite outcome. For CIAKI, a recent meta-analysis reported a pooled relative risk of 0.62 (95% CI: 0.45-0.86) favoring bicarbonate when compared to saline, with the individual study effect sizes ranging from 2% to 92%. There were too few studies that systematically tracked other clinical outcomes to reliably analyze the risks for dialysis (RR=0.51, 95% CI: 0.17-1.51) or death (RR=0.83, 95% CI: 0.32-2.19). Similar results have been reported for NAC. The Planning Committee felt that a 25% effect size would be clinically meaningful and within the range of what might be expected from previous studies, since the reduction in 90 day clinical outcomes is likely mediated by a reduction in CIAKI, which available literature suggests is reduced by as much as 92%.

Therefore, considering Model 2, we postulate that:

- Under control conditions, the 90-day event rate for our primary outcome (MAKE-D) is 8.7%
- Each of the two interventions will prevent 25% of these events
- Under each intervention condition, the 90-day event rate is 6.52%
- The absolute effect of each intervention will be a 2.18% reduction in 90-day events

We have two primary hypotheses, one for each main effect in the model. We will therefore allocate the type I error of 5% equally across the two interventions, assigning a type I error of 2.5% to each. Including a third test for the interaction term from the set of primary hypotheses would slightly decrease the statistical power. We discuss the potential impact of the interaction on the power of the study later in this section. One interim analysis using an O’Brien-Fleming rule will be carried out when half the expected number of MAKE-D events have occurred.

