**Table 10 - Sample size for selected response rates**

| Rate in control (C) group | Rate in treatment (T) group | % reduction (C -T)/C | Total sample size 80% power b | Total sample size 90% power b |
|---------------------------|-----------------------------|----------------------|--|--|
| 7.0                       | 4.90                        | 30%                  | 5,030                                    | 6,562                                    |
| 7.0                       | 5.25                        | 25%                  | 7,432                                    | 9,688                                    |
| 7.0                       | 5.6                         | 20%                  | 11,924                                   | 15,546                                   |
| 8.7                       | 6.1                         | 30%                  | 3,995                                    | 5,196                                    |
| 8.7 a          | 6.52 a           | 25% a     | 5,900 a                       | 7,680 a                       |
| 8.7                       | 7.0                         | 20%                  | 9,440                                    | 12,317                                   |
| 10.4                      | 7.3                         | 30%                  | 3,271                                    | 4,285                                    |
| 10.4                      | 7.8                         | 25%                  | 4,844                                    | 6,314                                    |
| 10.4                      | 8.3                         | 20%                  | 7,763                                    | 10,123                                   |

a rates and sample size for proposed model (with adjustment for losses to follow-up)

b adjusted for an O'Brien-Fleming stopping rule with one interim and one final test of hypothesis and considering a two-sided type I error = 0.025.

Thus, based on a 90 day event rate of 8.70% in the control group (i.e., saline or placebo) and

[name], [name]: CSP#578 “Prevention of Serious Adverse Events Following Angiography”  

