### **G. Interim analysis**

Using the O’Brien-Fleming procedure, we will carry out an interim analysis after half the expected number of events (292 events) has occurred, roughly after 18 months, to determine if either intervention shows a substantial beneficial effect. We will compare the proportion of subjects with a MAKE-D event with and without the use of bicarbonate and will compare the proportion of subjects with a MAKE-D event with and without the use of NAC. The respective absolute differences are dBicarbonate and dNAC. At the interim analysis, a z-value of 3.18 will be needed to reject the null hypothesis with Type I error of 2.5%. At the final analysis a z-value of 2.25 will be needed to reject the null hypothesis with Type I error of 2.5%.

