These estimations assume no interaction between the two active interventions, are adjusted for an O'Brien-Fleming stopping rule with one interim and one final test of hypothesis, and allow for an overall two-sided type I error of 2.5% for each hypothesis being tested. Hence, each of the interim hypothesis for main effect will be tested at p=0.001 level (allowing for 0.1% Type I error), and each of the final hypothesis for main effect will be tested at p=0.024 level (allowing for 2.4% Type I error).

If an attenuation of effect is present due to interaction between Sodium Bicarbonate and NAC, adjustment to the statistical power for 10% to 50% attenuation are given as follows.

Table 5. Statistical Power in the Presence of Effect Attenuation.

% attenuation from interaction between Bicarbonate & NAC	Rate in Bicarbonate/NAC	Rate in treatment (T) group	Rate in control (C) group	% reduction (C-T)/C	Power
No interaction	5.60 %	6.52%	8.7%	25%	90%
10% attenuation	5.78%	6.62%	8.7%	23.9%	87.5%
20% attenuation	5.97%	6.71%	8.7%	22.9%	84%

30% attenuation	6.15%	6.81%	8.7%	21.7%	79.3%
50% attenuation	6.53%	6.99%	8.7%	19.7%	69.4%

Sample recruitment and subsequent event rates will be summarized and presented to the DMC bi-annually as outlined in section 7 below. These reports will be used for monitoring the progress of the study and any modification to the recruitment schedule or the statistical analysis plan will be at the recommendation of the DMC.

5. Statistical Methods

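### A Holm step-down across the two co-equal primary hypotheses would keep the plan's 5% error and raise power to show both effects from about 82% to 89%; the fixed 2.5% split is valid, so this is a cheap improvement, not a correction of an error.

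*SAP*

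**What the plan says.** Protocol section V gives the two questions the same standing: "Each of these two hypotheses are of equal importance". Protocol section XVII.A.2, under Model 2, sets the error budget: "We will therefore allocate the type I error of 5% equally across the two interventions, assigning a type I error of 2.5% to each".

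SAP section 4 carries this forward. The sample-size assumptions "allow for an overall two-sided type I error of 2.5% for each hypothesis being tested"; at the interim "each of the interim hypothesis for main effect will be tested at p=0.001 level", and at the end "each of the final hypothesis for main effect will be tested at p=0.024 level". SAP 5.3.2 and 5.6 apply the 0.024 and 0.001 levels to each coefficient separately. Protocol section XVII.G gives the boundaries as z = 3.18 (interim) and 2.25 (final).

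Neither document has a step-down, Holm or other rule that passes alpha from a rejected hypothesis to the remaining one. The stated 90% power is per hypothesis; neither document states power to show both effects. The only other alpha rule for the primary analysis is in SAP 5.3.3: if the interaction test is significant at 0.05, the four subgroup tests are done at an overall level of 0.048.

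**The concern.** The plan itself sets a family-wise limit of 5% over two hypotheses. Once one null hypothesis has been rejected at its 2.5% boundary, only one can still give a false claim, and testing that one at 5% keeps the family-wise error within the limit. The plan keeps it at 0.024. If one intervention succeeds and the other ends with a final p-value between 0.024 and about 0.048, the plan supports no superiority claim for the second, although its own error budget would allow one. In a trial that treats both questions as equally important, the power to answer both is worth having when it costs only wording.

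**Working it through.** **Inputs.** Event rates 8.70% v 6.52%, 90% power, 7,450 evaluable patients and 7,680 with 3% loss (Protocol XVII.F, Table 10 and the text after it); 1:1 allocation at each margin and no interaction (SAP section 4); boundaries z 3.18/2.25 (Protocol XVII.G) or p 0.001/0.024 (SAP section 4); 1,000 additional non-VA patients (SAP section 2).

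**The plan's own figure.** Two-sided comparison of two proportions with pooled variance, p1 = 0.0870, p2 = 0.0652, mean 0.0761:
- √(2 × 0.0761 × 0.9239) = 0.3750 and √(0.0870 × 0.9130 + 0.0652 × 0.9348) = 0.3747.
- n per margin = [(2.2414 × 0.3750 + 1.2816 × 0.3747)/0.0218]², about 3,671, so N = 7,342 at alpha 0.025. At alpha 0.024, N = 7,406. The plan's 7,450 is within 2% of both, and 7,450/0.97 = 7,680.
- Power at N = 7,450: 90.45% at alpha 0.025 (call this L) and 94.40% at alpha 0.05 (call this H).

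The plan's sample size and power therefore reproduce.

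**Power to show both effects, single-look formulas.** In the balanced factorial the two marginal tests are practically uncorrelated (simulated correlation about 0.00).
- Fixed split: L² = 0.9045² = 81.8%.
- Holm: both p-values at most 0.05 and at least one at most 0.025, so H² − (H − L)² = 0.8911 − 0.0016 = 89.0%.
- At least one effect, either rule: 1 − (1 − L)² = 1 − 0.0091 = 99.1%.
- Per-hypothesis power under Holm: L + L(H − L) = 0.9045 + 0.9045 × 0.0395 = 94.0%.

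**With the two looks.** The pair 3.18/2.25 spends 2.50%; the corresponding 5% O'Brien-Fleming pair is 2.797/1.977 (final p about 0.048). Simulation of the four cells:

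| True state | Quantity | Fixed split | Holm |
|---|---|---|---|
| Both reduce events by 25% | both shown | 81.8% | 88.8% |
| Both reduce events by 25% | at least one shown | 99.1% | 99.1% |
| Only one works | power for that one | 90.4% | 90.5% |
| Only one works | false claim for the inert one | 2.5% | 4.8% |
| Neither works | any false claim | 4.9% | 4.9% |

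The 4.8% also follows from the single-look formula: 0.025 + 0.9045 × 0.025 = 0.0476. It falls to about 4.6% if an interim value may not be used retrospectively after a rejection at the final look; power is then almost unchanged. With the SAP's 0.001/0.024 as the first step, the result is still about 82% v 89%.

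**With the non-VA patients.** Assuming that they add to 7,680 with 3% loss: 8,680 × 0.97 = 8,420 evaluable, L = 93.72%, H = 96.51%. Both shown: 0.9372² = 87.8% v 0.9651² − 0.0279² = 93.1%.

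**The case against.** The strongest reply is that the sponsor chose the split openly, powered each hypothesis at 90% on that basis, and never set a target for showing both effects. Holding each question at 2.5% regardless of the other is defensible in a trial meant to settle the role of each intervention separately. Under Holm, a positive result for one intervention nearly doubles the false-claim rate for the other if that other is inert. All of this stands. It settles the status of the point (an option for the sponsor), but not the arithmetic: 4.8% is still inside the 5% total that the plan sets.

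The gain also depends on both interventions working. If only one works, its power barely changes, and with the non-VA patients the gain is about 5 points, not 7.

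Two stronger readings are tempting. A reader might infer that the plan wastes alpha and so contains an error. It does not: a fixed split controls the 5% and is conservative. A reader might also infer that an intervention with p between 0.024 and 0.048 would be declared ineffective. SAP 5.3.2 attaches no such conclusion to p above 0.024, and SAP 5.3 has the odds ratio, 95% interval and p-value reported either way.

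Last, a step-down confined to SAP 4, 5.3.2 and 5.6 leaves the interaction branch undefined, and the error rates above leave out the interaction pre-test. Adopting z = 3.18 in the SAP would also loosen its interim level, since 3.18 is p of about 0.0015 against the stated 0.001. Both points stand and are met in the fix.

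**Conclusion.** The plan is valid as written, and a Holm step-down would improve it at almost no cost. It keeps the family-wise error at or below 5% and raises power to show both effects by about 7 points (82% to 89%) with 7,450 evaluable patients, or about 5 points (88% to 93%) if the non-VA patients are added with 3% loss.

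These figures assume a true 25% reduction from each intervention, no interaction, and analysis by the main-effects model. The chance of at least one positive finding stays at about 99%. The sponsor has to accept a false-claim rate of up to about 4.8%, in place of 2.5%, for an inert intervention when the other works.

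**What to change.** Before unblinded results are seen, amend SAP 4, 5.3.2 and 5.6:

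1. **First step.** Keep the SAP's levels for each hypothesis (p = 0.001 interim, p = 0.024 final), or first reconcile them explicitly with the protocol's z 3.18/2.25.
2. **Second step.** Once either hypothesis is rejected, test the other, at that look and later, against the two-look 5% O'Brien-Fleming boundaries: z about 2.80 at the interim and 1.98 at the end (p about 0.048, not a flat 0.05).
3. **Scope.** State that the step-down applies only to the main-effects model in 5.3.2, and that the overall 0.048 rule in 5.3.3 governs if the interaction test is significant.

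Sample size, data collection and conduct do not change. The costs are the SAP wording, the higher error rate for an inert second intervention, and the fact that a simple per-hypothesis interval does not map exactly to the second decision. The last is small here: the sample code in SAP section 6 builds its 95% interval with 1.96, close to the 1.98 boundary.

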The power calculation for determining the total sample size depends only on these two main effect hypotheses. This means that the exploratory analyses do not have any associated power analyses. The primary analysis will -firstly test the significance of the interaction term, bicarbonate\*NAC. In the event of a non-significant interaction term at p=0.05 level, the regression model will be refitted without the interaction term. Otherwise, a stratified analysis will ensue where logistic models with single binary predictors for different levels of bicarbonate and NAC will be refitted. We will carry out the primary analysis by means of multivariable logistic regression without adjustment for any additional covariates.

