6.52% in the treatment group (i.e., bicarbonate or NAC), an absolute difference of 2.18% and a relative difference of 25%, we would need 7,450 patients to test the primary hypotheses with 90% power, assuming a type I error of 2.5% (splitting the alpha equally between the two primary hypotheses) without accounting for loss to follow up. Accounting for 3% lost to follow up, we

would need 7,680 patients. For the NAC intervention, the description above is entirely analogous.

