**Model 2 with Interaction Resulting in Complete Attenuation**

|         | Bicarbonate | Saline |       |
|---------|-------------|--------|-------|
| NAC     | 7.45%       | 7.45%  | 7.45% |
| Placebo | 7.45%       | 9.95%  | 8.7%  |
|         | 7.45%       | 8.7%   |       |

In this scenario, the overall effect at the margins would be reduced from a 25% reduction in MAKE-D events with each treatment to slightly more than a 14% relative reduction in events as demonstrated in the model above. This decrease in effect size would result in a reduction in the statistical power of the study to 40% with the proposed sample size of 7,680 patients; the total sample size would need to be increased to over 18,900 subjects to restore statistical power to 80% under these conditions. Fortunately, such an attenuation of effect of our interventions has not been observed in trials that have utilized both agents for the prevention of CIAKI. However, the possibility of a smaller attenuation of benefit cannot be excluded as the result of an interaction between bicarbonate and NAC. The impact of lesser degrees of interaction between the two interventions is illustrated in Table 11 below. These calculations are based on assumptions of a 25% reduction in MAKE-D events with bicarbonate (compared to saline) and NAC (compared to placebo); a baseline rate of events in the patients treated with both bicarbonate and NAC of 5.6% assuming no interaction/attenuation of effect; an overall sample size of 7,680 individuals equally allocated to each treatment arm; an estimated loss to follow-up rate of 3%; and a type I error of 2.5%.

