**Table 11 - Impact of Interaction between Bicarbonate and NAC on Statistical Power**

| % attenuation from interaction between Bicarbonate & NAC | Rate in subjects assigned to Bicarbonate/NAC | Rate in treatment (T) group | Rate in control (C) group | % reduction (C-T)/C | Power |
|--|--|-----------------------------|---------------------------|---------------------|-------|
| No interaction   | 5.60 %                                       | 6.52%                       | 8.7%                      | 25%                 | 90%   |
| 10% attenuation  | 5.78%  | 6.62%                       | 8.7%                      | 23.9%               | 87.5% |
| 20% attenuation  | 5.97%  | 6.71%                       | 8.7%                      | 22.9%               | 84%   |
| 30% attenuation  | 6.15%  | 6.81%                       | 8.7%                      | 21.7%               | 79.3% |
| 50% attenuation  | 6.53%  | 6.99%                       | 8.7%                      | 19.7%               | 69.4% |

Thus, the study will retain nearly 80% statistical power with the proposed sample size of 7,680 patients even if an interaction between bicarbonate and NAC leads to a 30% attenuation of their combined effect.

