3.9. Safety Data

The safety information to be collected for this study include the description of the event, distinction between serious and non-serious adverse event, severity and expectedness of the event, relatedness to the study intervention, and outcome of the event. In addition, data on all events will be classified using the Medical Dictionary for Regulatory Activities (MedDRA) (Version 9.0) coding dictionary.

Safety data will be collected for all consented subjects from the date the consent was signed up to 35 days post index angiography procedure for non-serious adverse events, and up to 90 days post index angiography procedure for serious adverse events. If the subject terminates from the study prior to 90 days post index procedure, collection of safety data will cease on termination date.

For reporting to the DMC and inclusion in the final report safety data will be aggregated for the ITT sample only as described in **3.3**. Data will be summarized as follows.

- Frequency and percentages of all non-serious and serious adverse events overall and by intervention group
- Frequency and percentages of all unique subjects with non-serious and serious adverse events overall and by intervention group
- Rates of non-serious and serious adverse events overall, by intervention group, and by center, calculated as # events/ person-time in years

- Tabulation of event type, MEDRA classification, severity, expectedness, relatedness and outcome of all events overall and by intervention group
- Overall hospitalization, dialysis, and mortality rate at 90 days and 1 year overall and by intervention group

4. Sample Size and Power

With a total sample of 7680 subjects equally allocated to each of 4 treatment arms, CSP 587 is powered to detect at least a 25% reduction in the 90-day incidence of MAKE-D for each intervention. Expected event rates used in sample size estimation to achieve 90% statistical power for hypothesis testing are given in Table 4 below. Justification for selecting these rates to estimate sample size and power are provided in the protocol.

Table 4. Expected 90-day Incidence of MAKE-D Endpoint

	Bicarbonate	Saline		
NAC	5.59%	7.46%	6.52%	Overall event rate 7.6%
Placebo	7.46%	9.95%	8.70%	
	6.52%	8.70%		

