5.3.3. Presence of Interaction

In the event of a significant interaction at $p=.05$ level, a stratified analysis will ensue where logistic models with single binary predictors for different levels of X_1 and X_2 will be refitted as follows

In NAC subgroup:	$\text{Log (Odds (MAKE-D))} = \alpha + \beta_{1a} X_1$	(Model 3)
In Placebo subgroup :	$\text{Log (Odds (MAKE-D))} = \alpha + \beta_{1b} X_1$	(Model 4)
In Bicarb subgroup:	$\text{Log (Odds (MAKE-D))} = \alpha + \beta_{2a} X_2$	(Model 5)
In Saline subgroup:	$\text{Log (Odds (MAKE-D))} = \alpha + \beta_{2b} X_2$	(Model 6)

Where X_1 is the indicator for the IV intervention (1=Bicarb, 0=Saline), and X_2 is the indicator variable for the oral intervention (1=NAC, 0=Placebo).

The parameter β_{1a} will estimate the independent effect of Bicarb compared to Saline among those allocated to NAC, β_{1b} will estimate the independent effect of Bicarb compared to Saline among those allocated to Placebo, β_{2a} will estimate the independent effect of NAC compared to Saline among those allocated to Bicarb, and β_{2b} will estimate the independent effect of NAC compared to Placebo among those allocated to Saline.

The efficacy of Bicarb relative to Saline and NAC relative to Placebo will be tested in each of the 4 subgroups at $p=0.048$ overall.

Based on the parameter estimates, the magnitude and direction of any interaction will be evaluated.

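### The power tables assume the pooled test is always made; under the plan's interaction rule the pooled claim has about 87% power, not 90%, and about 59%, not 69.4%, at 50% attenuation

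*SAP*

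**What the plan says.** **Power.** Protocol XVII.F says that "we would need 7,450 patients to test the primary hypotheses with 90% power" before loss to follow-up, and 7,680 after allowing 3%. SAP section 4 repeats the 90% for 7,680 subjects. For attenuation of the combined effect, the SAP says that "adjustment to the statistical power for 10% to 50% attenuation are given as follows", and its Table 5 matches Protocol Table 11. Below Table 11 the protocol concludes: "Thus, the study will retain nearly 80% statistical power", for 30% attenuation at the planned sample size.

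**What the power refers to.** Protocol XVII.A.1: "The power calculation for determining the total sample size depends only on these two main effect hypotheses". SAP section 2 defines the two primary hypotheses as pooled comparisons: groups 1+3 against 2+4 for bicarbonate, and groups 1+2 against 3+4 for NAC.

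**What the analysis does.** SAP 5.3.1 tests the interaction first, at 0.05. SAP 5.3.2 fits the pooled Model 2, tested at 0.024, only if the interaction is non-significant. Otherwise, under SAP 5.3.3, "a stratified analysis will ensue where logistic models with single binary predictors for different levels of" the two treatment indicators, at an overall level of 0.048. Protocol XVII.A.1 has the same rule. The interim analysis (SAP 5.6) tests Model 2 at 0.001 and assumes no interaction, so it is not subject to the rule.

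**The concern.** The power tables and the analysis rule describe different procedures. The tables give the power of the pooled comparison on the margins. The rule makes that comparison at the final analysis only if a preliminary test allows it. Even with no interaction, the preliminary test is significant in about 5% of trials by chance. With real attenuation it is significant more often, so the scenarios that Table 5 is meant to cover are those in which the tabulated test is more often set aside.

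Table 5 and Table 11 are where a reader learns how well the trial withstands an interaction. If they are read as the chance that the plan delivers its two primary hypotheses, they are too high in every row, and the gap grows with attenuation.

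**Working it through.** **Inputs.** 7,450 evaluable (Protocol XVII.F), so 3,725 per margin and about 1,862 per cell. Control margin 8.70%; treatment margins 6.52, 6.62, 6.71, 6.81 and 6.99% (Table 5). Cell rates 9.95, 7.46 and 7.46%, with the combination cell at 5.59, 5.78, 5.97, 6.15 and 6.53%. Two-sided 0.025 per main effect, interaction test at 0.05, interim at 0.001, final at 0.024.

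**Step 1: reproduce the stated power.** Power = Φ(z − 2.241), where z = (pC − pT) / √{[pC(1 − pC) + pT(1 − pT)] / 3,725}.

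- No interaction: z = 0.0218 / 0.00614 = 3.55; Φ(1.31) = 90.5% (stated 90%).
- 30% attenuation: z = 0.0189 / 0.00619 = 3.05; Φ(0.81) = 79.1% (stated 79.3%).
- 50% attenuation: z = 0.0171 / 0.00623 = 2.75; Φ(0.50) = 69.3% (stated 69.4%).

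The 10% and 20% rows give 87.2% and 83.6–83.7% (stated 87.5% and 84%). The tables are therefore pooled power with no preliminary test.

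**Step 2: how often the interaction test is significant.** The interaction log odds ratio is logit(p both) − 2·logit(0.0746) + logit(0.0995). Its standard error is √Σ 1/[1,862·p(1 − p)] over the four cells.

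- No interaction: 0.007 / 0.178 = 0.04; P(p ≤ 0.05) = 5.0%.
- 30% attenuation: 0.108 / 0.176 = 0.62; Φ(0.62 − 1.96) + Φ(−0.62 − 1.96) = 9.4%.
- 50% attenuation: 0.172 / 0.174 = 0.99; Φ(0.99 − 1.96) + Φ(−0.99 − 1.96) = 16.7%.

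**Step 3: power for the pooled claim under the rule.** The interaction test and the main-effect test are nearly independent. The interim is not subject to the rule, so

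P(pooled claim) ≈ P(interim crossing) + [pooled power − P(interim crossing)] × [1 − P(interaction significant)].

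The interim crossing probability at half the information is Φ(z/√2 − 3.29).

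- No interaction: 0.218 + (0.905 − 0.218) × 0.950 = 0.870.
- 30% attenuation: 0.129 + (0.791 − 0.129) × 0.906 = 0.729.
- 50% attenuation: 0.089 + (0.693 − 0.089) × 0.833 = 0.592.

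**Step 4: simulation of the rule.** 931 then 1,862 patients per cell, Wald tests from Models 1 and 2, interim at 0.001, final at 0.024. The last column also counts a claim in at least one stratum, at an assumed 0.012 per stratum test.

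| Attenuation | Stated | Always pooled | Interaction significant | Pooled claim under the rule | Any primary route |
|---|---|---|---|---|---|
| None | 90% | 90.4% | 5.0% | 86.8% | 90.8% |
| 10% | 87.5% | 87.1% | 5.7% | 83.2% | 87.7% |
| 20% | 84% | 83.1% | 7.2% | 78.2% | 84.2% |
| 30% | 79.3% | 79.1% | 9.4% | 72.8% | 80.8% |
| 50% | 69.4% | 68.5% | 16.7% | 58.5% | 72.8% |

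With all 7,680 evaluable, the pooled claim under the rule has 87.7% with no interaction and 59.8% at 50% attenuation. If the interim is ignored, at 7,448 evaluable, it has 85.9% and 57.2%.

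**The case against.** The strongest reply has three parts.

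*The tables are right and their basis is disclosed.* The first half stands: nothing in Table 5 or Table 11 is miscalculated. The protocol ties power to the main effects (XVII.A.1). It also remarks in XVII.A.2 that adding an interaction test to the primary hypotheses would lower power slightly. But it gives no figure, and the later discussion of interaction in XVII.F quantifies only the diluted margins, not the effect of the preliminary test. A loss of 10 to 11 points at 50% attenuation is not slight.

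*The stratum models are part of the primary analysis.* This also stands. SAP 5.3.1 sends the primary analysis to 5.3.3 when the interaction is significant. A reader might infer from 59% that this is the chance of any positive primary finding at 50% attenuation. The documents do not support that: counting a claim in either stratum gives about 73%, and the any-route figures are at or above the stated ones in every row. A single-stratum claim is, however, narrower than the pooled hypothesis in SAP section 2. Its power also rests on an assumed alpha, because SAP 5.3.3 does not say how 0.048 overall is divided among the four tests.

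*The design-case gap is small.* It is, at about 3 points. The larger gap needs 50% attenuation, where the pooled test is still made in about 83% of trials.

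**Conclusion.** The point holds as a mismatch between the stated power and the decision rule. For the pooled claim that the documents power, the plan as written delivers about 87, 83, 78, 73 and 59%, against the stated 90, 87.5, 84, 79.3 and 69.4%. The probability of a claim by any primary route is about 91, 88, 84, 81 and 73%, if each stratum test is made at 0.012.

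These results assume the documents' cell rates, 7,450 evaluable patients, an interim outside the rule, and no pooled test at the final analysis once the interaction is significant. SAP 5.3.3 provides for no such pooled test.

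Two further inferences are not supported. The sample size calculation is not wrong, since the stated figures reproduce on their own basis. Nor must the pooled test always be made: whether to test a pooled effect after a significant interaction is a legitimate design choice.

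**What to change.** 1. In SAP section 4 and Table 5, and in Protocol XVII.F and Table 11, label the existing figures as unconditional power of the pooled test.
2. Beside them, add the probability of the pooled claim under the interaction rule (about 87, 83, 78, 73 and 59%) and the any-route probability (about 91, 88, 84, 81 and 73%), with the stratum alpha assumed for the latter.
3. State in SAP 5.3.3 how the overall 0.048 is split across the four stratum tests, and recompute the any-route column if it is not 0.012 each.
4. Amend the sentence below Protocol Table 11 so that, at 30% attenuation, it gives about 73% for the pooled claim under the rule.

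The sponsor may instead choose to make the pooled Model 2 test always at the final analysis, with the interaction and stratum estimates reported beside it. The stated figures would then apply as they are. That changes the primary analysis, so it is an option and not a required correction.

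The cost is wording in both documents and a less favourable stated power for the pooled claim. No extra patients are needed, and items 1, 2 and 4 change no test.
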